- 2: prohibit EMS personnel from using cellular/mobile, smartphones during shifts
- 3: prohibit EMS personnel from viewing study related materials (education materials) during shift work
- 4: agencies that do not operate within the United States

Inclusion criteria for individual EMS personnel:

- 1: 18 years of age or older
- 2: Currently working as an EMS clinician
- 3: Working a minimum of one shift a week
- 4: Working & residing in the United States
- 5: Working at one of the EMS organizations that agreed to participate in this study
- 6: Have a cellular, mobile, or smartphone that can send and receive text messages
- 7: Willing to answer online surveys and respond to text-message queries for seven days in a row every third week of the month for a total of 24 weeks/6 months

Exclusion criteria for individual EMS personnel:

- 1: Individuals <18 years of age
- 2: Not currently working as an EMS clinician
- 3: Does not work a minimum of one shift a week
- 4: Does not work and/reside in the United States
- 5: Does not work at one of the EMS organizations that agreed to participate in this study
- 6: Does not have a cellular, mobile, or smartphone that can send and receive text messages
- 7: Is not willing to answer online surveys and respond to text-message queries for seven days in a row every third week of the month for a total of 24 weeks/6 months.

Children will not be enrolled in this study. EMS organizations employ licensed/certified EMS clinicians. In order to be an EMS clinician licensed or certified by states within the United States, individuals must be 18 years of age or older.

Power analysis:

With a 40 total EMS agencies enrolled (20 intervention and 20 wait-list control), and with a minimum of 10 participants per agency completing the study, we have 88% power to detect 0.4 standard deviation difference in the mean PSQI. With this level of enrollment, we have 90% power to detect a 20% difference in self-reported fatigue as measured by the CFQ.

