All enrollment procedures will take place on the study website (<https://www.emssleephealth.pitt.edu>). First, the individual EMS clinician will be taken to the video-based consent webpage. There he/she will play the consent video and then decide if he/she wants to follow through with enrollment. If he/she decides to enroll, then he/she will click on "(I ACCEPT) I have watched the informed consent video and agree to participate." OR - if he/she decides NOT to enroll, then he/she will click on the second option: "I DO NOT ACCEPT and do NOT want to participate in this research study."

For those who ACCEPT, they will then be taken to a new webpage on the study website that ask if they agree that all of the criteria for enrollment are TRUE. These criteria include all of the items asked on the screening page. This added step will provide final confirmation that the person signing up meets all criteria for enrollment.

For those who agree that all are TRUE, they will be taken to a webpage where they will type/enter in the name of their EMS Agency, their cellular/mobile phone number, and email address. Our study website is designed to cross-validate the agency name against a list that we maintain of EMS agencies that have agreed to participate. This verification takes place in real-time.

The individual's cellular/mobile phone number and email address will be used to

[1] get the individual EMS clinician registered with our automated text-messaging data collection system developed internally by the WPIC Office of Academic Computing;

[2] to email the individual a paper-based copy of the consent documentation; and

[3] to email the individual his/her temporary password to use when first logging into the study website where he/she will create a unique account and personalized password.

Next, the individual will receive four welcome text messages that say: "Welcome to the EMS Sleep Health Study" "You should receive an email with your password and instructions very soon." "REMEMBER: DON'T TEXT WHILE DRIVING." "If you received this message in error, please reply with one word: STOP."

Next, the participant will begin to answer the baseline survey located on the study website.

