Once the baseline is complete, the participant will be instructed to visit the shift schedule calendar component of the study website and enter in his/her shift schedule starting on the first Sunday following enrollment and include any shifts during a 7 consecutive days. This action will inform the automated text-message system to send the participant unique text-message based queries daily over a 7 consecutive days. After those 7 consecutive days, he/she will not receive any text messages for two full weeks (minus a few reminder text messages). This process of one week with text message queries followed by two weeks with no text message queries will be repeated for the duration of the study (6 months).

As described above, all individuals affiliated with EMS agencies randomized at baseline to the intervention group will have access to the study materials following completion of the baseline survey -- available on the study website. All individuals affiliated with EMS agencies randomized to the wait-list control group will have access to the study intervention materials at 3 months.

Consent procedures

Waiver to document consent approved.

Potential participants will view the video-based consent materials that will be made available on the study designed website.

Potential participants will be allowed to rewind and watch the consent video multiple times if needed. They can also email or call the study team prior to selecting the ACCEPT or DO NOT ACCEPT options for consent.

Our consent video will provide a detailed description of the study. Potential participants will be allowed to rewind the video and watch multiple times. They can also communicate directly with the study team via email or telephone prior to deciding to ACCEPT or DO NOT ACCEPT consent.

We have also added the screening items to appear one more time after the individual watches the consent video. He/she must then CONFIRM that all of the screening items / eligibility criteria are TRUE. This added step will help to ensure the potential participant is aware of the study criteria.

Our study is nationwide, which makes it difficult to obtain written informed consent from all study participants. We will still obtain consent from the study subjects via a video-based procedure, which does not increase risk.

Data safety monitoring

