Our study team will report on progress with recruitment, enrollment, data collection, and any unexpected issues to the Department of Emergency Medicine's Departmental Clinical Research Meeting (DCRM).

Protecting privacy

Only members of our research team are involved in this study protocol. No research findings will be provided to participant family members, insurance companies, employers, or any third party without the participant's authorization. All data that we collect for this research study will be assigned an ID number when received by our computerized data collection system. We will maintain a data file that contains the participant's name, mobile telephone number, and email address. This file will be located on a computer server and kept separate from the other data. This file will be password protected and access to this file will be restricted to core members of the research team. We will publish the study findings in aggregate in peer-reviewed medical journals.

Termination, withdrawal, or attrition

If a participant has not responded to study related text messages over multiple weeks, the study team will attempt to contact the participant to determine if he/she is still participating. If the attempts to contact the participant are unsuccessful, the participant may be classified as "withdrawn" or "lost to attrition," and his/her account on the study website will be suspended.

If a participant withdraws from the study, we will reach out to the participant with a standard email or telephone call. That email or telephone call will [1] acknowledge the participant's withdrawal; [2] thank the participant for his/her time commitment to the study period to withdrawing; and [3] extend an offer to the participant to contact the study team any time with questions. Our study does not have a category of partial withdrawal.

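### In the protocol text supplied, the only stated safeguard against texting while driving is one welcome text at enrolment, although daily text queries then recur one week in three for six months

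*Combined protocol and SAP*

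**What the plan says.** Under Research activities, a person who enrols gets a short set of messages: "Next, the individual will receive four welcome text messages that say", followed by the four texts. The third is "REMEMBER: DON'T TEXT WHILE DRIVING". The baseline survey comes next, and after it the participant enters shifts in a calendar starting from the first Sunday after enrolment.

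The calendar tells the automated system to "send the participant unique text-message based queries daily over a 7 consecutive days". The section adds that the process of "one week with text message queries followed by two weeks with no text message queries will be repeated" for the six months of the study. The two quiet weeks are free of messages "minus a few reminder text messages", whose content is not given.

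The individual inclusion criteria word the schedule differently. Criterion 7 asks for willingness to respond for "seven days in a row every third week of the month for a total of 24 weeks/6 months". Criterion 3 sets a minimum of one shift a week.

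The exclusion criteria for EMS agencies rule out those that "prohibit EMS personnel from using cellular/mobile, smartphones during shifts", and those that bar staff from viewing study material during shift work.

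Data safety monitoring is a single sentence. The team reports on recruitment, enrolment and data collection, and on "any unexpected issues to the Department of Emergency Medicine's Departmental Clinical Research Meeting (DCRM"). It names no crash, injury or other safety event.

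**The concern.** A reminder about driving makes sense only if the team thought participants might handle study texts at the wheel. The reminder is sent once, before the first query. The queries it is meant to cover then return every three weeks for half a year, in both arms.

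The setting makes this worth a second look. Participants work for agencies that run ground ambulances and must allow phones on shift. Background and Specific Aims describes more than half of EMS personnel as reporting poor sleep and fatigue, and links these to higher odds of injury. There is also some pressure to reply: willingness to answer is an entry criterion, and under Termination, withdrawal, or attrition a long silence leads to contact from the team and, if that fails, possible withdrawal and account suspension. No section says that a reply may wait until the vehicle is parked, or times queries away from driving.

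What is at stake is participant safety. The primary analysis is not touched.

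**Working it through.** The plan gives no count of query days, so there is no figure to reproduce. The count follows from the stated schedule.

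**Inputs**
- Days per query week: 7 (Research activities).
- Cycle: 1 week on, 2 weeks off, so 3 weeks (Research activities).
- Length: 24 weeks, also given as 6 months (individual inclusion criterion 7). Six calendar months is about 26 weeks.
- Minimum work: 1 shift a week (individual inclusion criterion 3).
- Driving warning: 1 text, at enrolment (Research activities).

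**Formulas**
- Query weeks = number of 3-week cycles started within follow-up.
- Query days = 7 × query weeks.
- Query days after the first query week = query days − 7.
- Shift days among the query days, at the minimum = 1 × query weeks, counting each shift as one day.

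**Results per participant**

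| Reading of the schedule | Query weeks | Query days | After first query week | Shift days at 1 shift a week |
|---|---|---|---|---|
| 3-week cycle, 24 weeks | 24/3 = 8 | 8 × 7 = 56 | 49 (49/56 = 88%) | 8 |
| 3-week cycle, 26 weeks | 9 started | 9 × 7 = 63 | 56 (56/63 = 89%) | 9 |
| Third week of each month, 6 months | 6 | 6 × 7 = 42 | 35 (35/42 = 83%) | 6 |

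On the 3-week cycle, the second query week starts three weeks after the first. The 49 later query days therefore all fall at least three weeks after the warning.

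The number of shift days depends on how much a person works. Above the minimum of one shift a week the documents give no figure. Taking 2, 3, 4 and 5 shifts a week as assumptions, the 8 query weeks would contain 16, 24, 32 and 40 shift days. How many query texts arrive during a shift, or while someone is driving, cannot be derived: the calendar informs the text system, but the timing of queries relative to shifts is not stated.

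The two wordings of the schedule do not agree (42 days against 56 to 63) and should be reconciled. The timing point is the same under each: one warning, before at least 83% of the query days.

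**The case against.** Several stronger readings are tempting, and the documents do not support them.

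- *That on-shift queries run for 56 days.* The 56 counts every query day, on or off shift. At the eligibility minimum only 8 are shift days, and excluding agencies that ban phones on shift says nothing about phone use at the wheel. The share of participants who drive is not given.
- *That the welcome text is the only safeguard in the trial.* The consent video and the emailed consent copy are not reproduced, and neither are the query texts or reminders. Any of them could repeat the warning. The absence can be asserted only for the supplied text. A warning in the consent material would still leave the timing as it is, since that too is given at enrolment; a warning within the query texts would largely answer the point.
- *That the protocol names texting while driving as a study risk.* It has no risk section. That the team foresaw the hazard is a fair inference from the reminder, but it is an inference.
- *That a crash would fall outside the monitoring rule because it was foreseen.* The sentence also covers data collection, and in ordinary usage a crash while answering a study text is an unexpected issue. It defines no narrower meaning of the word. What remains is that no safety event is named.
- *That 49 of 56 days measures the hazard.* It measures timing. Any instruction given once at enrolment precedes most of the follow-up, and no document shows that the effect of this one fades or that repeating it lowers risk.

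All these objections stand against the stronger readings. None removes the narrower fact: the supplied text gives the warning once, and the messages it concerns keep coming for months.

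**Conclusion.** The point holds as a low-cost safety improvement. In the supplied text one driving warning, at enrolment, stands against about 56 query days per participant over 24 weeks (42 to 63 across readings of the schedule).

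The conclusion assumes full participation for the stated period, and assumes that the unseen query and reminder texts carry no driving warning of their own. It also rests on the judgement that a reminder given near the exposure is more useful than one given weeks or months before; that is plausible but not shown here. No harm is documented, exposure while driving cannot be quantified, and no estimate, sample size or analysis changes. The brevity of the monitoring sentence is missing detail and does not carry the finding.

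**What to change.** In the Research activities paragraph that sets out the text-message cycle, state that the automated system sends the existing driving warning as the first text of every 7-day query week, in addition to the welcome text. If the query or reminder texts already contain it, say so in the protocol instead.

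The cost is one automated message per query week: about 8 per participant (6 to 9 across the readings above), on a system that already sends reminders. The downside is slightly more messages. While editing, reconcile the schedule wording between individual inclusion criterion 7 and Research activities.

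As an optional clarification only, Data safety monitoring could say that safety events related to participation, such as a crash while handling a study text, are among the matters reported to the departmental meeting. That is a one-line change. It would not by itself create a way for participants to disclose such an event.

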Per-protocol analyses will be used to determine if variation in exposure to the intervention materials (education modules) is associated with a change in outcomes of interest. Hierarchical mixed effects models will be used to account for clustering at the agency level and the dependence between repeated measures at the participant level to characterize the relationship between exposure to the education module intervention and the outcomes of interest among participants who engage with the intervention and had an outcome assessment after intervention exposure. We will use Bonferonni corrected p-values when multiple comparisons are examined to test a study hypothesis. All

analyses will be performed with the SAS statistical software version 9.4 (Cary, North Carolina).

Research activities:

We will begin recruitment by disseminating the EMS Agency Flyer (paper-based version initially) to various EMS agency email listservs and distribution lists (e.g., ask the National Association of State EMS Officials to email their agency members).

Next, we will screen EMS agencies that respond to our study flyers to determine eligibility.

All EMS agencies will be randomized to either the intervention group or the wait-list control group. All agencies and individuals affiliated with the agencies randomized to the intervention group will have access to the study educational materials on the study website (<https://www.emssleephealth.pitt.edu>) once the individuals create their own account. All individuals randomized to the wait-list control group will receive access to the study educational materials - which are accessible on the study website.

Next, we will ask the EMS administrators to circulate a paper-based Research Study Flyer directly to the individual EMS clinicians using email and direct person-to-person distribution - AND -- to circulate a video-based version of the Research Study Flyer.

Next, we will instruct the individuals to visit our study designated website and follow the steps for screening (<https://www.emssleephealth.pitt.edu>). If after following the steps for screening the individual is eligible, he/she will then follow the instructions on the website for enrollment.

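### The withdrawal rules provide no survey-only status and may close the route to PSQI and CFQ follow-up for participants who are silent on texts and cannot be reached

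*Combined protocol and SAP*

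**What the plan says.** The section Termination, withdrawal, or attrition sets out a sequence. A participant who has not answered study texts for an unspecified number of weeks prompts the team to make contact and ask whether he or she is still taking part. If contact fails, the team has discretion to class the person as having withdrawn or been lost, and the stated consequence is that "his/her account on the study website will be suspended". For participants who withdraw, the section describes a courtesy email or call and ends with the statement "Our study does not have a category of partial withdrawal".

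The individual inclusion criteria name two tasks in one item: "Willing to answer online surveys and respond to text-message queries for seven days in a row". Under Research activities, the participant is emailed a temporary password "to use when first logging into the study website where he/she will create a unique account and personalized password". After the welcome texts, "the participant will begin to answer the baseline survey located on the study website". The same section gives intervention-arm staff access to the educational materials "once the individuals create their own account".

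Specific Aims names the PSQI and the CFQ as the two primary outcomes. The Statistical analysis plan says that the primary analyses follow intention to treat, using mixed models with random intercepts that handle agency clustering and repeated measures.

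**The concern.** The primary outcomes are questionnaires. The rule that can end a person's participation is triggered by a different channel, the text messages. Someone may tire of a week of daily queries, repeated through the study, and still be willing to complete a PSQI and a CFQ. The plan has no status for that person.

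The plan also allows a person to be recorded as withdrawn who never asked to leave. That blurs refusal with non-contact in the participant flow.

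At stake are later PSQI and CFQ assessments on randomized participants. Intention to treat is best served by seeking those assessments from everyone who has not declined. A mixed model uses whatever was observed, but it cannot recover an assessment that was never sought.

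**Working it through.** The plan gives no figure on this point, so the check is a comparison of sections.

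**Step 1. Who is affected.** Reading the withdrawal section case by case:

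| Participant | What the plan provides |
|---|---|
| Silent on texts, reached, still taking part | No change; account stays open |
| Silent on texts, not reached | May be classed as withdrawn or lost to attrition; account suspended |
| Asks to stop texts only | No status, because partial withdrawal is ruled out |
| Asks to leave altogether | Withdrawn; courtesy contact |

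The point concerns the second and third rows only. In the second row the classification is discretionary, and survey response is not part of the trigger.

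**Step 2. Does suspension close the PSQI and CFQ route?** Three statements suggest that it does:

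- The account is the website login (Research activities).
- The baseline survey is on the website and comes after the password email in the described order (Research activities).
- The surveys are described as online (individual inclusion criteria).

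No statement says when, or by what channel, the follow-up PSQI and CFQ are collected. The link is therefore an inference. The consent material is not part of the public text and may settle it.

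**Step 3. What the analysis would lose.** Nothing says that data collected before withdrawal or suspension are discarded, and the mixed model can use them. The possible loss is confined to later assessments. The document describes no survey collection after withdrawal or suspension and no alternative route for the PSQI and CFQ.

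**Step 4. Which parts depend on the inference.** The missing survey-only status (third row) does not depend on Step 2, because it follows from the withdrawal section alone. The loss of primary-outcome access through suspension (second row) does depend on it.

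**Step 5. Size.** A figure would need the number of participants who go silent and cannot be reached, the timing of the PSQI and CFQ assessments, and the relation of silence to arm and outcome. The documents give none of these, so no size or direction can be computed.

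**The case against.** The strongest reply is that the rule is milder than it looks. Silence leads first to a contact attempt. A person who is reached and says that he or she is still taking part keeps the account, even if the texts go on unanswered, which is an informal survey-only path. Those who are not reached have ignored both texts and contact attempts, so few of them would be likely to answer a survey invitation. Willingness to do both tasks is an entry criterion, so the absence of partial withdrawal may be deliberate. And the harm from suspension rests on an unstated link.

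Most of this stands. It limits the point to people who ask to stop only the texts and people who cannot be reached, and it makes modest recovery the realistic expectation. It does not remove the point. An informal path for people who happen to be reached is not a recorded status for those who ask, and willingness at entry does not require surveys to end when texts stop.

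A reader might infer three stronger things that the documents do not support:

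- **That text silence alone ends survey follow-up.** Failed contact is also required, and classification is then discretionary.
- **That the weeks of follow-up lost can be counted from the query schedule.** The number of silent weeks is undefined. Research activities describes one week of queries followed by two without, whereas the inclusion criteria can be read as a monthly pattern. Any such count would also measure website access, not PSQI or CFQ assessments.
- **That the rule biases the treatment effect or undermines the stated power.** The documents give no dropout rate and no relation between silence and outcome. The power statement is already framed in completers per agency.

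**Conclusion.** The point holds in a limited form. As a matter of text, the plan has no recorded status for a participant who stops texts and continues surveys, and it can label an unreached person as withdrawn without a request to leave. On the assumption that follow-up PSQI and CFQ surveys use the website account, text silence plus failed contact also closes the route to primary-outcome data that the intention-to-treat analysis would use.

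How many people this touches, and whether any bias follows, cannot be determined from the documents. Severity is minor: the rule is a stated design choice that can be improved cheaply. It is neither a contradiction nor a calculation error.

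**What to change.** Replace the sentence on partial withdrawal and the suspension clause with wording such as:

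> A participant may stop text messages and continue surveys; this is recorded as 'stopped texts, continues surveys'. Survey access is not suspended for text non-response or failed contact, and PSQI/CFQ survey invitations continue to the contact details held until month 6 unless the participant asks to leave data collection. Non-contact is recorded as lost to attrition, and 'withdrawn' is used only when the participant asks to leave.

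The contact details already exist. Under Protecting privacy the plan says "We will maintain a data file that contains the participant's name, mobile telephone number, and email address".

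The costs are real but small:

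- Research activities lists three uses for the phone number and email address, and survey invitations are not among them. An IRB modification and a consent wording update are therefore probable.
- The compensation section pays $5 at enrollment and $5 each month. The team must decide how the monthly payment applies to survey-only participants.
- Some invitations will go unanswered, and recovery among people who have already not replied to contact attempts is likely to be modest.
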